## V. Nutrition

a) What is the patient's height?

b) What is the patient's current weight?

c) What is the patient's weight approximately 6 months ago?

d) Calculated Body Mass Index:

**Body Mass Index=Weight/(Height)**

e) Percent Unintentional Weight Loss:

**% unintentional weight loss =**

IRB Protocol No. 15342  
04/30/19

Version Date:

Version: 23

Page 121 of 145

**(unintentional weight lost in last 6 months/baseline body weight) x 100**

**VI. Labs: (performed within 4 weeks of this assessment)**

- a) Creatinine: \_\_\_\_\_
- b) Hemoglobin: \_\_\_\_\_
- c) Albumin: \_\_\_\_\_
- d) Liver Function Tests: Normal or Not normal \_\_\_\_\_
- e) WBC: \_\_\_\_\_
- f) CA125 (Gynecological patients ONLY): \_\_\_\_\_
- g) Blood Urea Nitrogen: \_\_\_\_\_

**VII. Scoring**

- a) Did the patient score  $\geq 11$  on the Blessed Orientation-Memory-Concentration Test (see previous page)?

- No
- Yes (if yes, notify the patient's treating physician)

**VIII. Was the patient able to complete “Geriatric Assessment – Patient Questionnaire” on his/her own?**

Yes     No

If no, why? (Mark all that apply with an X.)

- Not literate (does not read or write)
- Visual problem
- Fatigue
- Questions too difficult (above the patient's reading ability)

Other: specify \_\_\_\_\_

## **IX. Time to complete**

a) Appendix H (Questionnaires to be completed by the study participant)

Start Time: \_\_\_\_\_

End Time: \_\_\_\_\_

b) Appendix I (Data to be gathered by the healthcare team)

Start Time: \_\_\_\_\_

End Time: \_\_\_\_\_

**Total time to complete Appendix H and I:** \_\_\_\_\_

Name of person completing this document: \_\_\_\_\_

Signature: \_\_\_\_\_

Date: \_\_\_\_\_

## **APPENDIX J: SAE/UP Reporting Coversheet**

### **NOTIFICATION OF UNANTICIPATED PROBLEM/SERIOUS ADVERSE EVENT**

#### **For Use by Participating Institutions Only**

THIS FORM ALONG WITH A COPY OF THE MEDWATCH 3500A FORM MUST BE EMAILED TO [[contact]](mailto:[contact])  
WITHIN 24 HOURS OF KNOWLEDGE OF ONSET OF SERIOUS ADVERSE EVENT OR UNANTICIPATED  
PROBLEM

**COH IRB # (insert once IRB number known) - Participating Site IRB # \_\_\_\_\_**

Staff Submitting Form:	Date:
Phone No.:	Email:

Reporting Investigator:	
Event:	
Participant ID:	Institution:
Date Event Met Reporting Criteria (as defined in protocol):	

Type of Report:  Initial  Follow-up

CTCAE Grade:  G1/mild  G2/moderate  G3/severe  G4/life threatening  
 G5

Attribution to Neratinib:  Unrelated  Unlikely  Possible  Probable  Definite

Meets Definition of Serious AE:  Serious  Non-serious

Meets Definition of Unanticipated Problem:  UP  Not a UP

Has the event been reported to the participating institution's IRB?  No  Yes

Date: \_\_\_\_ / \_\_\_\_ / \_\_\_\_ (If yes, please attach report to this submission)

## **APPENDIX K: Patient Instructions For the Management of Diarrhea**

**Please review these instructions with your study doctor/team. Once all of your questions are answered, sign at the bottom and make sure you are given a copy of these instructions to take home.**

Diarrhea is the most common side effect you may have while participating in this study. Diarrhea usually starts within a few hours to a few days of the first dose of study drug. In order to reduce or even prevent diarrhea as far as possible, you will be supplied with an anti-diarrheal medicine called loperamide to take at the start of the study. **Use of anti-diarrheal medication is required for all enrolled subjects to help reduce or prevent diarrhea.** Loperamide will be dispensed directly by your study doctor/team on day 1 with the instruction to initiate treatment with loperamide at the same time as you take your first dose of neratinib.

**Start taking the anti-diarrheal medication immediately with the first dose of neratinib as directed by your study doctor/team.**

Your study nurse/team will call you 1 day, 2 days and 3 days after your first dose of study drug to find out if you are experiencing diarrhea and to provide further treatment instructions and advice if necessary. You will also have an easy to follow flow-chart to help you each day in the management of diarrhea if it is present.

If you are having new-onset diarrhea, persistent diarrhea or diarrhea with increase of 4 or more stools per day over usual, call your study nurse /team at phone number

\_\_\_\_\_ to let them know so they can work with you to control the diarrhea.  
If you are dizzy or weak because of diarrhea, call your study nurse/team immediately. If you are unable to reach assistance, please seek medical attention immediately.

Please record the number of stools and any anti-diarrheal medication taken during all Cycles of the study along with the daily dose of study medication in your diary and return the completed diary at the next scheduled visit.

### **Information to provide when talking to your doctor**

When talking to the study doctor/team I will provide as much of the information below as possible, in order to help my study doctor/team to assess my diarrhea and decide on the best treatment:

- Number of stools per day as compared to my normal bowel habits
- Presence of diarrhea during the night
- Presence of fever, dizziness, abdominal pain/cramping, or weakness
- What the stool looks like, that is, watery stools, blood, or mucus

- When I took my last study drug
- Any other information that could explain my diarrhea (food, recent travel, contact with other people with diarrhea).

#### Medications to treat diarrhea

My study doctor/team will provide me with loperamide on day 1 with the instruction to start treatment with loperamide along with the first dose of neratinib. I need to take the medications as directed by my study doctor/team.

Loperamide:

- I will initially take 2 tablets/capsules (4 mg) with the first dose of neratinib
- Thereafter, I will take 2 tablet/capsule (4 mg) three times a day for the next two weeks; if I get constipated, I should contact my study doctor/team who will instruct me on how often and how much loperamide to take but I should not stop taking loperamide.
- After the first two weeks, I will take 2 tablet (4 mg) twice a day onwards through the first 1cycle of therapy (28days) from the start of neratinib regardless of whether I have diarrhea or not.
- If I continue to have diarrhea while taking loperamide, I should contact my study doctor/team for additional anti-diarrheal medication and consult.
- If I have diarrhea with increase of up to 6 stools per day over usual any time after completing the two cycles of therapy and I am not taking any anti-diarrheal medication, I will take 2 tablets/capsules (4 mg) immediately after the first loose stool and then 1 tablet (2 mg) every 4 hours or after each loose stool to a maximum dose of 8 tablets/capsules (16 mg) in any 24 hour period until I haven't had any loose stool for at least 12 hours.

Other medication (Study doctor/team to write in name of medication and instructions):

---

---

---

In case of more severe diarrhea and any diarrhea associated with fever, pain, infection, or dehydration, I may receive IV fluids, antibiotics and/or other medications

---

---

---

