**Table 5: Loperamide Dosing**

Day	Loperamide Dose
1	4mg at time of first dose of neratinib, then 12mg in 3 divided dose of 4mg tid
2-14	Daily dose of 12 mg in 3 divided doses of 4 mg tid
15-28	Daily dose of 8 mg in 2 divided doses of 4 mg bid
29+	Daily dose as needed (not to exceed 16 mg per day)

Patients must use a diary to record intake of loperamide. Loperamide pill counts will be conducted during the first 2 cycles (56 days) of therapy.

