**Table 6: Loperamide Dose Reduction Levels for Constipation**

Dose Level	Loperamide Dose	Tablets/Capsules per Day
0	4 mg TID	6 tablets/capsules a day
-1	4 mg BID	4 tablets/capsules a day
-2	2 mg TID	3 tablets/capsules a day
-3	2 mg BID	2 tablets/capsules a day
-4	2 mg once a day	1 tablet/capsule a day

Abbreviations: BID = twice daily; mg = milligrams; TID = three times daily

The Investigator/study nurse must review with the patient the **patient instructions (Appendix K)** for the management of diarrhea and the **Patient Diary (Appendix M)** for the patient's daily recording of investigational product during the first 2 cycles, number of stools, and use of loperamide and/or other anti-diarrheals. Both the patient and the Investigator/study nurse must sign the patient instructions for the management of diarrhea. The Patient Instructions and Patient Diary are to be handed to the patient before leaving the site with investigational product on or before Cycle 1/Day 1, with clear instructions to contact the Investigator in the event of *de novo* onset or persistent Grade  $\geq 2$  diarrhea to discuss the appropriate course of treatment.

An “Optimal Management of Diarrhea Checklist” (**Appendix L**) will be reviewed and signed by study investigator or study nurse on Cycle 1 Day 1. The study team will call patients at 1 day, 2 days and 3 days after first dose of neratinib to assess tolerance.

Documentation of any occurrences of stools or diarrhea must be as precise as possible and captured in the Patient Diary. For AE recording, documentation of “intermittent” events of diarrhea is limited to Grade 1. If events of Grade 1 diarrhea are separated by 3 days without any diarrhea, then each event must be documented as separate AEs with corresponding start and stop dates.

The entries on the Patient Diary should be reviewed together with the patient for the first 2 cycles. If the patient has experienced diarrhea since the last visit, details of the daily number of stools provided on the diary help to grade the diarrhea as precisely as possible (per NCI CTCAE v.4.0). Also, the daily dose of loperamide (or other anti-diarrheals, if applicable) noted on the diary for patients in the neratinib treatment will be reviewed and recorded on the CRF.

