#### *7.6.1.3 New onset uncomplicated Grade 1 or Grade 2 diarrhea for Cycle 2 and beyond*

##### **Dietetic measures:**

- Stop all lactose-containing products.
- Drink 8 to 10 large glasses of clear liquids per day.
- Eat frequent small meals.
- Recommend low fat regimen enriched with bananas, rice, applesauce and toast until resolution of diarrhea.

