##### **Pharmacological Treatment:**

- Administer loperamide: initial dose of 4 mg (2 tablets/capsules) with the first bout of diarrhea followed by 2 mg (1 tablet/capsule) every 4 hours or after every unformed stool (maximum 16 mg a day) and continue loperamide at this frequency until diarrhea free for 12 hours.
- For patients with persistent Grade 1 diarrhea on loperamide, Lomotil (diphenoxylate hydrochloride and atropine sulfate) 1 tablet (2.5 mg) every 6 to 8 hours may be added (or equivalent as approved by the Sponsor).
- For Grade 2 diarrhea (4 to 6 stools per day above baseline, despite intensive antidiarrheal therapy), consider adding octreotide (short-acting) 150 µg SC three times daily (TID); or after initial dose of short-acting octreotide, if well tolerated, a single dose of octreotide LAR 20 mg intramuscular (IM) (equivalent medication may be used with approval of the Investigator).

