### 1.2.1 Study Medication adjustments

If I am experiencing loose stools or diarrhea and cannot reach my study doctor/team immediately, I will start taking anti-diarrheal medication per the instructions above until further advice is given by my study doctor/team. If I have more than 4-6 stools per day compared to normal despite taking anti-diarrheal medication for 24 hours, and I cannot reach my study doctor/team, I will stop taking the study medication and wait for further instructions from my study doctor/team.

My signature below indicates I have reviewed this information and have received the following medications:

- Neratinib Tablets
- Loperamide

---

Study participant name

Study participant Signature and Date

---

Investigator delegate name

Investigator delegate Signature and Date

OR

---

Investigator name

Investigator Signature and Date

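### Appendix K, the patient's take-home diarrhea sheet, delays self-started loperamide until after two cycles, while the protocol body starts the same regimen in Cycle 2

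*Combined protocol and SAP*

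**What the plan says.** Section 7.6.1.1 makes loperamide prophylaxis mandatory on a fixed schedule through Day 28. After that it is taken as needed, up to 16 mg a day. Section 7.6.1.2 repeats this, and the Day 29+ row of Table 5 agrees.

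Section 7.6.1.3 covers treatment once fixed dosing has ended. Its heading reads "New onset uncomplicated Grade 1 or Grade 2 diarrhea for Cycle 2 and beyond". The loperamide instruction under it is an "initial dose of 4 mg (2 tablets/capsules) with the first bout of diarrhea followed by 2 mg (1 tablet/capsule) every 4 hours" or after each unformed stool, up to 16 mg a day, until the patient has been free of diarrhea for 12 hours.

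Appendix K is the patient's copy of these rules. Section 7.6.1.1 gives it formal standing: "Both the patient and the Investigator/study nurse must sign the patient instructions for the management of diarrhea". Three parts of the sheet matter here:

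- The fixed schedule runs "through the first 1cycle of therapy (28days) from the start of neratinib regardless of whether I have diarrhea or not".
- The last loperamide bullet gives a self-start dose for an increase of up to 6 stools a day over usual, but only "any time after completing the two cycles of therapy and I am not taking any anti-diarrheal medication".
- For a patient with loose stools who cannot reach the team, the sheet says: "I will start taking anti-diarrheal medication per the instructions above until further advice is given by my study doctor/team".

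The sheet also tells the patient to telephone the team: "If you are having new-onset diarrhea, persistent diarrhea or diarrhea with increase of 4 or more stools per day over usual" is the trigger.

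**The concern.** One regimen has two start dates, and the later one is on the only version the patient holds at home. Cycle 2 is the first period without scheduled prophylaxis, in a population that the synopsis describes as especially vulnerable to diarrhea. A patient in Cycle 2 who has stopped loperamide and develops loose stools should, under Section 7.6.1.3, take 4 mg at the first bout. Read as written, the sheet does not permit that dose until Cycle 3.

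The weak spot is the fallback. It exists for the patient who cannot get through to the team, and it relies on doses given higher up the sheet. In Cycle 2 the fixed doses have run out and the self-start dose is not yet allowed. What is at stake is a delay in a simple early treatment.

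**Working it through.** **1. Day ranges.** The study calendar sets cycles of 28 days. Two cycles are 2 × 28 = 56 days, which reproduces the 56 days that Section 7.6.1.1 gives for the loperamide pill counts. So Cycle 1 is Days 1 to 28, Cycle 2 is Days 29 to 56, and the period after two cycles starts on Day 57.

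**2. Are the two regimens the same?**

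| Element | Section 7.6.1.3 | Appendix K, last loperamide bullet |
|---|---|---|
| First dose | 4 mg | 4 mg (2 tablets) |
| Further doses | 2 mg every 4 hours or per unformed stool | 2 mg every 4 hours or per loose stool |
| Daily maximum | 16 mg | 8 tablets × 2 mg = 16 mg |
| Stop | 12 hours without diarrhea | 12 hours without loose stool |
| Severity | Grades 1 and 2 (up to 6 stools over baseline) | Up to 6 stools over usual |
| Start | Cycle 2, Day 29 | After two cycles, Day 57 |

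They agree on every row but the last.

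**3. What each source gives, by period.**

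| Period | Protocol body | Appendix K |
|---|---|---|
| Days 1–14 | 4 mg three times a day | 4 mg three times a day |
| Days 15–28 | 4 mg twice a day | 4 mg twice a day |
| Days 29–56 | As needed to 16 mg (7.6.1.1, 7.6.1.2, Table 5); treatment regimen (7.6.1.3) | No fixed dose; self-start dose not yet allowed |
| Day 57 on | As above | Self-start regimen |

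The uncovered interval on the sheet is 56 − 28 = 28 days. In the protocol body it is 0 days.

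**4. Which date is intended?** Sections 7.6.1.1 and 7.6.1.2, Table 5 and Appendix K's own schedule line all end fixed dosing at Day 28. Section 7.6.1.3 begins where that schedule stops. No other text in the documents supports a Day 57 start.

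**5. After correction.** If the bullet starts at Day 29, the interval on the sheet falls from 28 days to 0, and the sheet matches Section 7.6.1.3.

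**The case against.** A reader might infer that the trial has no written loperamide dose for Cycle 2. The documents do not support that. Sections 7.6.1.1, 7.6.1.2 and 7.6.1.3 and Table 5 all give one, and the dose-adjustment text in 7.6.1.1 tells staff to raise loperamide to as much as 16 mg a day for diarrhea in Cycles 1 and 2. The gap is confined to the patient's sheet.

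Even there, much softens it:

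- The sheet tells the patient to call about new diarrhea and to take medication as the team directs, and it has write-in lines for other drugs.
- The calendar has nurse toxicity evaluations on Day 1 and Day 15 of Cycle 2 and on Day 1 of Cycle 3. Diaries are reviewed with the patient, and loperamide is counted, through the first two cycles.
- The bullet concerns patients who are taking no antidiarrheal. Those still on loperamide come under the bullet before it, which sends them to the team.
- The sheet promises a daily flow-chart. It is not in the supplied text, so it may already carry a Cycle 2 dose.
- The fallback has no cycle limit of its own. A practical patient might simply use the only as-needed regimen printed above it.

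All of this stands, and it limits the harm to a possible delay. It does not make the start date right. The last argument asks the patient to ignore an explicit condition in a signed instruction. The flow-chart, whatever it shows, would leave the sheet in conflict with Section 7.6.1.3.

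**Conclusion.** The inconsistency is certain on the wording, and it is minor. For 28 days, the whole of Cycle 2, Appendix K gives no loperamide dose that applies, and its fallback for an unreachable team has none to point to. Every patient who starts Cycle 2 passes through this interval. It matters in practice only for those who are off antidiarrheals, develop diarrhea and cannot promptly reach the team. The documents do not let that number be estimated.

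A reader might also infer that the wording distorts the monitoring of grade 3 or higher diarrhea in Section 15.2.2, because Cycle 2 is 28 of the 56 days in its window. The documents do not support a claim of that kind. They give no figure for how a delay in loperamide changes the rate of severe diarrhea. Half of the days is also not half of the risk, since Section 7.6.1.1 places typical onset in the first few weeks. Tables 17 and 18, the endpoints and the sample size are unaffected.

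The conclusion assumes that the sheet is followed as printed and that nothing has been written in by the team. The content of the flow-chart is unknown.

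**What to change.** In the last loperamide bullet of Appendix K, change the time condition so that it reads *after completing the first cycle of therapy (from Day 29)*. Leave the dose, the maximum, the stop rule and the instruction to call the team as they are. The fallback then has a dose to refer to throughout treatment and needs no edit.

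Obtain IRB approval of the revised sheet and give it to patients on treatment at their next visit. If the flow-chart states a start date, check that it says the same.

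The cost is one phrase, one IRB submission and redistribution of the sheet. No patients, visits, procedures or analyses are added.

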### Changes to my diet to treat diarrhea

If I have diarrhea, I will:

- Stop all lactose-containing products (milk, yogurt, cheese, etc)
- Drink 8 to 10 large glasses of clear liquids per day
- Eat frequent small meals
- Eat low fat foods such as the BRAT diet that includes **bananas, rice, applesauce, and/or toast**:
  - The BRAT diet is a bland diet that is low in fat and fiber and will not irritate the stomach;
  - Bananas are high in potassium and can cause constipation which can help alleviate the diarrhea
  - Other similar foods are crackers, cooked cereals and pasta
  - This diet is not complete in nutrients and should only be taken for a short period of time and only upon the doctor's advice.

My study doctor/team may have other suggestions for me. (Study doctor/team to write in any suggestions).

### 1.2.1 Study Medication adjustments

If I am experiencing loose stools or diarrhea and cannot reach my study doctor/team immediately, I will start taking anti-diarrheal medication per the instructions above until further advice is given by my study doctor/team. If I have more than 4-6 stools per day compared to normal despite taking anti-diarrheal medication for 24 hours, and I cannot reach my study doctor/team, I will stop taking the study medication and wait for further instructions from my study doctor/team.

My signature below indicates I have reviewed this information and have received the following medications:

- Neratinib Tablets
- Loperamide

---

Study participant name

Study participant Signature and Date

---

Investigator delegate name

Investigator delegate Signature and Date

OR

---

Investigator name

Investigator Signature and Date

## APPENDIX L: Optimal Management of Diarrhea Checklist

---

**This checklist must be completed for each patient by study team (investigator or study nurse) during the Day 1 visit before the patient leaves the site with study medication.**

**Patient Number:** |\_\_\_\_\_|\_\_\_\_\_|\_\_\_\_\_|\_\_\_\_\_|\_\_\_\_|

**Day 1 Visit Date:** |\_\_\_\_\_|\_\_\_\_\_| / |\_\_\_\_\_|\_\_\_\_\_| / |\_\_\_\_\_|\_\_\_\_|

- I have communicated the risk and the timing of diarrhea occurrence to my patient while discussing the informed consent form and patient diarrhea instruction sheet.
- I have ensured that my patient takes home loperamide along with study medication.
- I have instructed my patient to take loperamide concomitantly with the first dose of neratinib and to take the prophylactic dose of loperamide 4mg three times a day for the next 14 days to minimize the occurrence and severity of diarrhea. Thereafter, continue to take loperamide 4mg twice a day as indicated in the protocol for first cycle (28 days).
- I have reviewed with my patient dietetic measures (e.g., hydration, low lactose, low fat diet enriched with bananas, rice, applesauce and toast) recommended in case he/she experiences loose stools or diarrhea.
- I have instructed my patient to record the number of daily stools, the occurrence of diarrhea and any anti-diarrheal treatment along with the daily dose of study medication in his/her diary daily for all cycles of study medication.
- I have informed my patient that he/she will receive a call at 1 day, 2 days and 3 days after first dose of study medication to assess his/her tolerance to the study medication and to document the date the first dose of study medication was taken.
- I will follow-up with my patient on severe diarrhea and other adverse events until resolution.

I checked with my patient that he/she can be reached at  
\_\_\_\_\_.

My patient has received my number and knows to call me as soon as he/she experiences loose stool or diarrhea (COH medical oncology call center: [contact]).

**Study CRA or Study Nurse's Name and Signature:**

---

---

Loperamide is the recommended standard therapy for diarrhea in this study. Additional treatment may be required. Refer to the protocol for other therapy and literature.

## APPENDIX M: Patient Diary

Date dd/mm /yy	Name of Drug	Time Taken	Dose Taken	# of Tablets per Day	# of Stools per Day	Comments on missed or reduced doses for Study Medication(s), any additional anti-diarrheal medication, and any symptoms (i.e. Diarrhea, Vomiting, Pain)
	Neratinib					
	Loperamide					
	Neratinib					
	Loperamide					
	Neratinib					
	Loperamide					
	Neratinib					
	Loperamide					
	Neratinib					
	Loperamide					
	Neratinib					
	Loperamide					
	Neratinib					
	Loperamide					
	Neratinib					
	Loperamide					
	Neratinib					
	Loperamide					
	Neratinib					
	Loperamide					
	Neratinib					
	Loperamide					
	Neratinib					

Date dd/mm/ yy	Name of Drug	Time Taken	Dose Taken	# of Tablets per Day	# of Stools per Day	Comments on missed or reduced doses for Study Medication(s), any additional anti-diarrheal medication, and any symptoms (i.e. Diarrhea, Vomiting, Pain)
	Loperamide					
	Neratinib					
	Loperamide					
	Neratinib					
	Loperamide					
	Neratinib					
	Loperamide					
	Neratinib					
	Loperamide					
	Neratinib					
	Loperamide					
	Neratinib					
	Loperamide					
	Neratinib					
	Loperamide					
	Neratinib					
	Loperamide					
	Neratinib					
	Loperamide					

